### 6.3.11 Virologic Studies

Plasma HIV-1 RNA Assay

Screening HIV-1 RNA must be performed within 90 days prior to study entry using an FDA-approved assay by a laboratory that possesses a CLIA certification or equivalent, and should be performed between 60 and 90 days prior to entry to optimally manage blood volume. Eligibility will be determined based on the screening value.

Entry and post-entry plasma HIV-1 RNA should be performed per the SOE. Samples should be processed and shipped to the designated central ACTG testing laboratory (refer to LPC for shipping information).

All occurrences of confirmed HIV viral loads above 200 copies/mL must be recorded on the eCRF.

Stored Plasma for HIV-1 RNA SCA

Plasma for HIV-1 RNA SCA will be obtained as required per the SOE and stored for batched analyses. The sample at entry for SCA must be collected prior to initiating cemiplimab/placebo infusion.

See the LPC located on the A5370 PSWP, for details on processing plasma samples for SCA.

The baseline SCA value will be the mean of the pre-entry and entry determinations, which must have been obtained at least 7 days apart.

CD4+ T cell-associated HIV-1 RNA

Cell-associated HIV-1 RNA will be measured in total CD4+ T cells isolated from cryopreserved PBMC obtained at pre-entry, prior to cemiplimab/placebo infusion at entry/day 0 and week 6, and thereafter per the SOE.

CD4+ T cell-associated HIV-1 DNA

Total HIV-1 DNA in total CD4+ T cells isolated from cryopreserved PBMC will be measured to normalize cell-associated HIV-1 RNA data, at pre-entry, prior to cemiplimab/placebo infusion at entry/day 0 and week 6, and thereafter per the SOE.

Stored PBMCs for Quantification of Intact Proviral Genomes

PBMCs will be stored for quantification of intact proviral genomes per the SOE. See the LPC for details on processing PBMC samples.

T cell-associated HIV-1 RNA: DNA Ratios

Cell-associated HIV-1 RNA: DNA ratios in total CD4+T cells isolated from cryopreserved PBMC will be calculated from the cell-associated HIV-1 DNA and RNA data described above.

HIV-1 Drug Resistance Genotype

An HIV-1 drug resistance genotype (virus population sequencing) will be performed at local CLIA-certified commercial laboratories in those individuals with confirmed virologic failure.

NOTE: Standard Plasma HIV-1 RNA Assay, CD4+ T cell-associated HIV-1 RNA, and CD4+ T cell-associated HIV-1 DNA are not necessary for participants who discontinue ART for any reason. After the start of infusion, for participants who

do not complete cemiplimab/placebo infusion, the necessity for these studies will be determined on a case-by-case basis in discussion with the core team. The duration of the infusion and the volume of cemiplimab/placebo infused should be recorded.

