## 6.0 CLINICAL AND LABORATORY EVALUATIONS

## 6.1 Schedule of Evaluations (SOE)

Table 6.1-1: SOE: Screening through Week 48

Evaluation	Screening	Pre-Entry	Entry/Day 0	Post-entry Evaluations (Weeks)													Premature Study Discontinuation (D/C) Visit	Confirm Virologic Failure (if needed)
				1	2	4	6	7	8	10	12	16	20	24	28	36	48	
Window	Between 60-90 days prior to entry	Between 30 and 50 days prior to entry	≤24 hours post-randomization	±2 days	-2/+7 days	±2 days	-2/+7 days											
FSH	X																	
Free Testosterone (male participants only)		X			X							X					X	X
Urinalysis			X				X				X			X			X	X
Pregnancy Testing	X		X	If suspected		X	If suspected		X	If suspected		X	If suspected		X	If suspected		If suspected
Metabolic Studies (see section 6.3.8)	X	X				X	X			X	X	X	X	X	X	X	X	
Adherence Assessment			X (see section 6.3.9)	X			X (see section 6.3.9)	X			X	X	X	X	X	X	X	X
CD4+/CD8+	X		X				X			X			X			X		X
Stored Plasma/PBMCs for Immunologic Studies		X	X		X	X	X		X	X	X	X	X	X	X	X	X	
Advanced Flow Analysis		X	X		X	X	X		X	X	X	X	X	X	X	X	X	
Standard Plasma HIV-1 RNA	X		X	X			X	X		X		X		X		X	X	X

Table 6.1-2: SOE for PK Evaluations - Pre-Entry through Week 48

Evaluation	Pre-Entry	Entry/Day 0		Week 1	Week 2	Week 4	Week 6		Week 7	Week 8	Week 10	Week 12	Week 16	Week 20	Week 24	Week 28	Week 36	Week 48	Premature Study Discontinuation	Confirm Virologic Failure (if needed)										
							±2 days																							
		Prior to infusion	Following infusion				Prior to infusion	Following infusion																						
Window	Between 30 and 50 days prior to entry	Within 15 min prior to infusion	Within 15 min following infusion	±2 days	-2/+7 days		Within 15 min prior to infusion	Within 15 min following infusion	±2 days	-2/+7 days																				
Cemiplimab Serum Concentrations 	X		X	X	X		X	X	X	X	X	X	X	X	X	X	X	X	X	X	X									
Stored Blood for Gene Expression Assays 		X		X		X	X		X		X	X	X	X	X		X				X									
Stored PBMCs for RO Studies 	X			X	X		X		X	X	X	X	X	X	X	X	X	X	X	X	X									
Stored Plasma for ARV PK Assays 		X			X	X	X			X	X																			
Anti-drug Antibody Detection Assays		X												X			X		X	X										

For participants who do not complete cemiplimab infusion, the necessity for these studies will be determined on a case-by-case basis in discussion with the core team. The actual date, and start and stop times of the infusion, and rate of infusion should be recorded.

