#### 6.2.5 Discontinuation Evaluations

Evaluations for Randomized Participants Who Do Not Start Study Treatment

Participants who withdraw from the study prior to starting study treatment/placebo should have entry/day 0 and off-study forms completed and keyed. No further evaluations or follow-up are required for these participants. Participants will be replaced. All eCRFs must be completed for the period up to and including entry/day 0.

Premature Treatment/Placebo Discontinuation Evaluations

Participants who begin but do not complete of both infusions of cemiplimab/placebo, but receive some of the investigational product, and are willing to stay on the study, will be followed for safety by completing all study visits and evaluations as outlined in the SOE. If one or both cemiplimab/placebo infusions have been administered, samples for serum cemiplimab, RO, and ADA will be collected per the SOE (duration of sampling in participants that do not receive or complete the second infusion will be decided on a case-by-case basis with the core team). Whether virologic, immunologic, and stored ARV plasma samples will be stored or performed following premature discontinuation of cemiplimab/placebo infusions will be determined on a case-by-case basis in discussion with the core team. The duration of the infusion (including actual start and stop times) and the volume of each cemiplimab/placebo infusion should be recorded. Participants who do not complete  $\geq 90\%$  of both infusions of cemiplimab/placebo will be replaced unless the participant has reached a protocol-defined safety endpoint. Participants who withdraw should be explicitly asked about the contribution of possible AEs to their decision to withdraw consent, and any AE information elicited should be documented.

Discontinuation of Antiretroviral Therapy

Participants who discontinue cART for any reason will be followed for safety by completing all study visits and evaluations as outlined in the SOE. If ART is discontinued prior to completion of cemiplimab/placebo infusions, then no further infusions should be given. Whether cemiplimab serum concentrations or RO assays will be collected following discontinuation of ART will be determined on a case-by-case basis in discussion with the core team. Stored plasma/PBMC for

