immunologic studies, stored plasma for SCA and samples for CD4+ T cell associated HIV-1 RNA, DNA, and 2-long terminals repeats (2-LTRs) do not need to be obtained for time points after the participant has discontinued ART.

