**6.3.9 Adherence Assessment**

A standardized assessment to monitor ART adherence will be administered per the SOE and will include assessment for ART interruption of more than 7 consecutive days. An interruption of more than 7 days will be considered treatment discontinuation. For ART discontinuation, see [section 6.2.5](#).

At Entry/Day 0 and week 6, the adherence assessment should be performed prior to infusion.

The adherence eCRF is posted on the DMC Portal in the Forms Management Utility.

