## 7.4 Study Monitoring

The Protocol Core Team will monitor the conduct and safety of the study via regular summaries by cohort pooled over treatment arms of accrual, baseline characteristics, study conduct (including premature study discontinuations and premature study treatment discontinuations), any missed doses of study treatment/placebo, any reported interruptions of ART, HIV-1 RNA levels  $\geq 200$  copies/mL (see [section 6.2.4/Confirmation of Virologic Failure](#)), data completeness, specimen collection, and AEs. The core protocol team will review the individual participant-level safety data frequently to assess the relation of all reported AEs to study treatment/placebo.

The DAIDS clinical representative will review and assess EAE reports for potential impact on the study participant safety and protocol conduct as per DAIDS policies, guidance documents, and SOPs, as applicable.

The study will undergo interim review at least annually by an independent ACTG-appointed SMC. The first review is anticipated to be review of the first cohort, regarding dose escalation to the second cohort. The SMC will review information by cohort on accrual, baseline characteristics, conduct of the study (including premature study discontinuations and premature study treatment discontinuations), AEs by treatment arm (including core protocol team assessment of relationship to study treatment), CD4+ T cell counts, virologic failures, and HIV-1 RNA levels/suppression over time by treatment arm, and completeness of follow-up and sample availability. In particular, irAEs will be monitored.

After the last enrolled participant in each cohort receives study treatment and completes follow-up through the week 12 visit and the blinded data become available for review by the core team, safety data including the core team decision on relation of AEs to study treatment will be reviewed by the SMC, unblinded to treatment arm, to determine whether to dose escalate or modify the study. Complementing the SMC reviews, a designated study chair or co-chair may notify the SMC of Grade 4 AEs or deaths, as well as notable Grade 3 AEs among the events that the sites email to the core team per section 8.0. An interim review may also be convened if a concern is identified by the DAIDS clinical representative, the study chairs, or study statisticians in consultation with the team. See also [section 10.4](#) for statistical considerations related to interim monitoring.

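### Two safety rules contradict each other in the protocol: whether plasma HIV-1 RNA continues after ART stops (6.3.11 against 6.2.5), and where Grade 2 ALT/AST begins (7.3.2 against 8.3.2)

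*Protocol*

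**What the plan says.** **HIV-1 RNA after ART stops**

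- Protocol 6.3.11, closing NOTE: "Standard Plasma HIV-1 RNA Assay, CD4+ T cell-associated HIV-1 RNA, and CD4+ T cell-associated HIV-1 DNA are not necessary for participants who discontinue ART", whatever the reason for stopping.
- Protocol 6.2.5, on what happens once ART is stopped: "Participants who discontinue cART for any reason will be followed for safety by completing all study visits and evaluations as outlined in the SOE". It then lists what may be dropped: stored immunology samples, plasma for the single copy assay (SCA), and "samples for CD4+ T cell associated HIV-1 RNA, DNA, and 2-long terminals repeats (2-LTRs) do not need to be obtained". Cemiplimab concentrations and receptor occupancy are left to case-by-case decision.
- Table 6.1-1 in 6.1 has a separate row for "Standard Plasma HIV-1 RNA", and the body of 6.3.11 states: "Entry and post-entry plasma HIV-1 RNA should be performed per the SOE".
- Protocol 6.3.9 sets the trigger and directs sites to 6.2.5: "An interruption of more than 7 days will be considered treatment discontinuation. For ART discontinuation, see" that section.
- Protocol 6.2.4 calls for an HIV-1 RNA retest no sooner than 2 weeks after ART restarts when non-adherence is confirmed.

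**Liver threshold**

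- Protocol 7.3.2 defines possible DILI by ALT and/or AST of at least Grade 2, with 3 x ULN or more given in parentheses as the meaning of that grade.
- Protocol 8.3.2 sets the expedited-reporting trigger for the same laboratory pattern, with Grade 2 running from 2.5 to below 5.0 x ULN. Section 8.3.2.2 repeats that range.
- The alkaline phosphatase limit (below 2 x ULN) and bilirubin limit (2 x ULN or more) are the same in both sections.

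**The concern.** On the first point, a site handling a participant who has been off ART for more than 7 days finds two instructions. Under 6.2.5 the viral load is still drawn. Under the 6.3.11 NOTE it may be skipped. Nothing says which prevails. The participants concerned are the ones most likely to be viremic. Section 7.4 has the core team summarise "any reported interruptions of ART, HIV-1 RNA levels" of 200 copies/mL or more, and has the SMC review "virologic failures, and HIV-1 RNA levels/suppression over time by treatment arm". Gaps in this subset would make both summaries less informative.

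The NOTE also does not say that testing restarts with ART. Read as a lasting waiver, it could be taken to cover the retest in 6.2.4.

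On the second point, a participant with ALT or AST between 2.5 and 3.0 x ULN who meets the other DILI conditions should prompt an expedited report under 8.3.2 but falls short of the number printed in 7.3.2.

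**Working it through.** The protocol has no planned figure to reproduce here. The check compares the sections and sizes the effect.

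**1. Is the assay exempt under 6.2.5?**

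| Status in 6.2.5 after ART stops | Samples | Count |
|---|---|---|
| May be dropped | stored immunology samples, SCA plasma, cell-associated RNA, cell-associated DNA, 2-LTR | 5 |
| Case by case | cemiplimab serum, receptor occupancy | 2 |
| Standard plasma HIV-1 RNA | in neither group | 0 of 7 |

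Because the assay is an SOE row and is not among the 7, the general rule in 6.2.5 keeps it. Section 8.7, for ART stopped between infusions, gives a similar list of research samples and also leaves this assay out. That supports the reading by omission only. The 6.3.11 NOTE alone adds the clinical viral load to the waived samples.

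**2. How many tests could be lost?**

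- The standard HIV-1 RNA row of Table 6.1-1 shows 11 marks. Removing screening and entry gives 11 − 2 = 9.
- Up to two of the remaining marks may belong to the event-driven columns (premature discontinuation, confirmation of failure), giving 9 − 2 = 7. Column alignment in the text available for review is broken, so the range is 7 to 9.
- This is a ceiling. A later stop exposes fewer tests, and a gap must exceed 7 days to count, so a test in the first week could rarely be affected.

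**3. How many participants?**

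The protocol gives no ART interruption rate. Assuming 2% to 10% of the 45 planned participants:

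- 0.02 × 45 = 0.9
- 0.10 × 45 = 4.5

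That is about 1 to 5 participants across the study.

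**4. How wide is the liver mismatch?**

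- Lower bound of Grade 2: 2.5 x ULN (8.3.2, 8.3.2.2) against 3.0 x ULN (7.3.2). Difference: 3.0 − 2.5 = 0.5 x ULN.
- Share of the Grade 2 interval: (3.0 − 2.5) / (5.0 − 2.5) = 0.20.

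The 20% is a share of the interval's width, not of expected cases. A case must also meet the bilirubin and alkaline phosphatase limits and have no other apparent cause.

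**5. Does any planned analysis move?**

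- The primary outcome (10.2.1.1), escalation criteria (10.4.1) and pause rules (10.5) do not use HIV-1 RNA or the DILI definition.
- Efficacy analyses (10.6.2) already use only measurements taken before a cART interruption of more than 7 days.
- Sample size and power are untouched.

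**The case against.** **HIV-1 RNA.** The best defence is that the 6.3.11 NOTE is a specific exception to a general rule, and that the list in 6.2.5 was never meant to be complete. The parallel NOTE in 6.3.10 also waives T-cell proliferation and gene expression samples, which 6.2.5 does not name. That is right: the 6.2.5 list is not strictly closed, so the assay's absence from it is not decisive alone. The NOTE also permits omission rather than requiring it, so a site that keeps drawing the sample complies with both sections. And the 6.2.4 retest is a direct, event-specific instruction that the NOTE does not expressly cancel. What remains is that a site may follow the NOTE in good faith and skip viral loads that 6.2.5 and the body of 6.3.11 place on the SOE.

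**Liver threshold.** Both sections rest on Grade 2 or above, and 7.3.3 makes the DAIDS grading table mandatory, so a site working from the grade would report correctly. DILI or hepatitis judged related to treatment is expedited as an adverse event of special interest (AESI) at any grade, and Grade 2 ALT/AST already leads to withholding and core-team contact under 8.3.2.2. These safeguards limit the harm. They do not remove the conflict: the AESI route depends on a judgement of relatedness, and 3 x ULN is not where this protocol's Grade 2 begins, whichever threshold was intended. It is also fair that the document does not prove which number the authors wanted.

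**Conclusion.** Both contradictions stand in the current text, and both are minor.

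The HIV-1 RNA conflict makes gaps possible, not certain. Under the assumed interruption rate it concerns about 1 to 5 of 45 participants, with no more than 7 to 9 tests each. The cost falls on safety monitoring of viral load, not on any planned inference.

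The liver mismatch affects a band 0.5 x ULN wide and matters only when the other DILI conditions are met and no other reporting route has already applied.

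The existence of the conflicts rests on the text alone. The participant count rests on the assumed 2% to 10% rate, and the test count on a schedule row whose column alignment could not be confirmed.

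**What to change.** 1. In the 6.3.11 NOTE, delete the standard plasma HIV-1 RNA assay from the waived tests, so that it continues per the SOE as 6.2.5 requires. At minimum, state that testing resumes when ART resumes, which protects the 6.2.4 retest. Adding the assay to the 6.2.5 exemptions would also end the contradiction, but it would thin the viral-load data that 7.4 relies on.
2. In 7.3.2, change the ALT/AST figure from 3 to 2.5 x ULN, to match the grade it names and 8.3.2. If 3 x ULN was the intended trigger, state that number in both sections without calling it Grade 2.

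The cost is wording only. The assay is already on the SOE, and no new visit or laboratory test is needed.

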#### 6.3.12 Pharmacokinetic Studies (refer to [section 11.0](#))

##### Cemiplimab Serum Concentrations

Blood will be collected for determination of cemiplimab in serum using a validated ligand binding assay. A pre-entry sample will be drawn. At entry/day 0 and week 6, samples are drawn within 15 minutes following infusion (and must be obtained from the contralateral arm), and within 15 minutes prior to the infusion on week 6. At weeks 1, 2, 7, 8, 10, 12, 16, 20, 24, 28, 36, and 48, samples can be drawn at any time during the visit. Record the date and actual time of dosing and of sample drawn in the eCRF.

##### Stored Blood for Gene Expression Assays

Samples will be collected for the gene expression analysis as per the SOE. Samples collected on infusion days (day 0 and week 6), should be collected pre-infusion. All samples that are collected may not be tested. Please refer to the LPC for specimen collection and processing instructions.

##### RO Studies

Cryopreserved PBMC samples will be used to assay PD-1 RO by cemiplimab by flow cytometry. At pre-entry and within 15 minutes prior to infusion at week 6, samples are drawn. At weeks 1, 2, 7, 8, 10, 12, 16, 20, 24, 28, 36, and 48, samples can be drawn at any time during the visit. Record the actual date and time of dosing and of sample drawn in the eCRF.

##### Stored Plasma for ARV PK Studies

At entry/day 0 (prior to infusion). At weeks 2, 4, 6 (prior to infusion), 8, and 10. Samples obtained on non-infusion days can be drawn during the participant's visit (a specific time of day is not required), documentation of the date and time samples are drawn is required in the eCRF. Documentation of the date and time of the 3 previous doses of all antiretroviral medication(s) are to also be recorded in the eCRF. Samples will undergo testing as indicated if the participant is viremic.

#### 6.3.13 Anti-drug Antibody (ADA) Assessments

Serum samples for the assessment of anti-cemiplimab antibody may be collected at Entry/Day 0 (prior to infusion), weeks 12, 24, 48, and at premature study discontinuation. Additional ADA samples may be collected at or near any suspected immune mediated adverse events of special interest (AESI) in collaboration with the investigator of record and A5370 core team.

On a case-by-case basis, in discussion with the core team, remaining serum from cemiplimab samples may be assessed for ADA, if deemed necessary based on the PK profile seen.

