### 3.0 STUDY DESIGN

This trial is a phase I/II, double-blinded (within each cohort), dose-escalating, placebo-controlled study of the safety and immunotherapeutic activity of two infusions of anti-PD-1 (cemiplimab) or placebo in HIV-1-infected participants on cART who have HIV-1 RNA below the limit of quantification and CD4+ T-cell counts  $\geq 350/\text{mm}^3$ . Cemiplimab (0.3 mg/kg [Cohort 1], 1 mg/kg [Cohort 2], and 3 mg/kg [Cohort 3]) or placebo will be given to 15 participants in each Cohort (12 active and 3 placebo). Participants will receive infusions of antibody or placebo at entry/day 0 and week 6, for a total of two infusions, with the primary safety endpoint through week 48 and the primary immunologic endpoint through week 12. The study will enroll sequential dose-escalating cohorts with the second and third cohorts receiving the first infusion after all participants in the previous cohort have reached week 12 and an evaluation of safety outcomes by the study team and the study monitoring committee (SMC) is completed, which determines whether to

dose escalate or not. Participants will be followed for 48 weeks with frequent safety evaluations.

Cemiplimab/placebo infusion will occur over 30 minutes via IV infusion. Safety data from Cohort 1 (first dose level) will be reviewed by the core team (blinded to treatment assignment) and an SMC, before higher doses are administered. Guidance criteria for the SMC with respect to dose escalation are described in [section 10.4.1](#). If the first dose level is well tolerated and the core team and SMC note no safety concerns, Cohort 2 will be enrolled after Cohort 1 reaches week 12. If the second dose level is well tolerated and the core team and SMC note no safety concerns, Cohort 3 will be enrolled after Cohort 2 reaches week 12. Immunologic and virologic response data from lower dose cohort(s) may not be available prior to the enrollment of the subsequent dose cohort(s).

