## 10.0 STATISTICAL CONSIDERATIONS

### 10.1 General Design Issues

A5370 is a phase I/II, double-blinded (within each cohort), dose-escalating, placebo-controlled study of the safety and immunotherapeutic activity of two infusions of anti-PD-1 (cemiplimab) in HIV-1-infected participants on cART who have HIV-1 RNA below the limit of quantification and CD4+ T-cell counts  $\geq 350/\text{mm}^3$ . Each participant will be followed for 48 weeks, with frequent visits in the first 12 weeks. The decision to enroll into each successively higher dose cohort will be based on review of the safety data seen in participants who received cemiplimab or placebo doses in the previous dose cohorts (see [sections 7.4](#) and [10.4.1](#)). Accrual for each dose cohort is anticipated to take 3-4 months. Taking into account the time needed for data review regarding dose escalation between each cohort (data entry, core team review, SMC report generation, and SMC review) and assuming that all three cohorts complete enrollment, the total time to complete accrual is expected to be about 20 months. This may take longer if participant replacements are needed. Laboratory assays and study analyses may commence, and findings reported, after each cohort has completed accrual and follow-up through the week 12 visit.

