#### 10.2.1 Primary Outcome Measures

##### 10.2.1.1 Safety

Occurrence of a Grade  $\geq 3$  AE, or Grade  $\geq 1$  irAE (such as, but not limited to, pneumonitis, colitis, adrenal insufficiency, or hypothyroidism), that is related to study treatment (as judged by the

core team, blinded to treatment arm) any time from study treatment administration through the week 48 visit.

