Descriptive summaries, by dose group, will be presented for the estimated PK parameters (see [section 11.0](#)). Graphical approaches will display concentration curves over time, as well as RO over time.

Designated staff at identified laboratories may be unblinded prior to database lock to facilitate bioanalytical analyses of pharmacokinetic samples and ex vivo immunogenicity studies.

The timing of treatment effects on immunologic and virologic outcome measures will be investigated by identifying, for each measure, the post-treatment timepoint with the greatest magnitude change from baseline. It is also of interest to evaluate whether there is evidence that the second dose of treatment further “boosts” responses following the first dose. For this reason, samples are collected at a comparable schedule following the first and second doses.

The associations between ex vivo HIV-specific T-cell responses following cemiplimab exposure (based on pre-treatment samples) and in vivo HIV-specific immune responses to treatment will be evaluated using Spearman correlations. Bioinformatics approaches will be used to evaluate changes in gene expression profiles before versus after treatment.

Regression models, graphical displays and correlation analyses will investigate dose-response relationships with respect to immunologic and virologic changes after treatment across the dose groups, and in relation to PK parameters estimated as outlined in [section 11.0](#).

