## 10.7 Unblinding

For unblinding requests, including emergency unblinding, refer to ACTG Standard Operating Procedure (SOP)-123, Unblinding Participants, (<https://member.actgnetwork.org/cms/folder/6184>).

In the event that emergency disclosure of treatment assignment is thought to be required, the site investigator must follow ACTG SOP- 123, Unblinding Participants.

- (1) Sudden (or unplanned) unblinding of one or more arms due to interim analysis results or results of another trial: The decision to unblind one or more arms of an ongoing study is made by the team in conjunction with the relevant Scientific Committee and the Executive Committee. This can occur based on a recommendation from the DSMB or an SMC or the results of another trial (also see the DAIDS SOP “Termination of a Trial or a Single Treatment Arm”).
- (2) Participant contact: If the decision is made to unblind, participants should be unblinded as soon as possible. Unblinding is conducted through the DMC, which sends treatment assignments to the sites soon after the unblinding decision. Every effort should be made by the sites to contact participants who have completed follow-up in order to explain the study results.
- (3) Implications of unblinding on study data: When a treatment comparison is unblinded based on an interim analysis, the results of that interim analysis must be reported in publications. Data from visits that occurred before the interim review but that were not in the database at the data cutoff date have little potential for bias and may be reported with a comment. Data from visits that occurred after unblinding are potentially biased and must not be used if the intent is to claim that all the data are from a blinded study. In unblinding due to both “interim analysis” and the “other trial results” situations, if analyses are reported on clinical data or samples taken after the unblinding date, the conditions under which these data were gathered must be made clear in any publication.

Unblinding will not occur to allow replacement of participants (see [section 6.2.5](#)). Premature treatment discontinuation, other than for a treatment-related AE, would result in an increase in the applicable limit for enrollment into the active or placebo arm (as appropriate) for the designated cohort by the ACTG randomization department.

All site e-mails to the team should be carefully worded to prevent unblinding the team, if possible.

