##### Peripheral RO

- Pre-entry sample
- Week 6 (within 15 minutes prior to infusion); any time during the visit at weeks 1, 2, 7, 8, 10, 12, 16, 20, 24, 28, 36, and 48.
- Determination of the need to assay certain/all samples will be based on the serum cemiplimab concentration seen. Samples obtained on non-infusion days can be drawn during the participant's visit (a specific time of day is not required); documentation of the date and time of dosing and of all RO samples drawn is required in the eCRF.

See [section 6.0](#) for details of sample collection.

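### Section 6.3.13 brings the blinded core team into ADA decisions based on an individual's cemiplimab PK profile; used before unblinding, this would in effect disclose that participant's arm to the body judging relatedness for the primary endpoint

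*Protocol*

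**What the plan says.** Section 6.3.13 schedules ADA samples at entry, weeks 12, 24 and 48, and at premature discontinuation. It then adds an option for leftover PK serum, to be decided one participant at a time: "in discussion with the core team, remaining serum from cemiplimab samples may be assessed for ADA, if deemed necessary based on the PK profile seen".

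The core team has another role. For the primary safety outcome (section 10.2.1.1), relatedness to study treatment is decided by the "core team, blinded to treatment arm) any time from study treatment administration through the week 48 visit". Section 7.4 shows that this is continuing, participant-level work: "The core protocol team will review the individual participant-level safety data frequently to assess the relation of all reported AEs to study treatment/placebo". Section 3.0 repeats the blinding for the dose-escalation review, where safety data are "reviewed by the core team (blinded to treatment assignment").

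Three further statements bear on timing and access:

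- Section 10.1: "Laboratory assays and study analyses may commence, and findings reported, after each cohort has completed accrual and follow-up through the week 12 visit".
- Section 10.6.2: "Designated staff at identified laboratories may be unblinded prior to database lock to facilitate bioanalytical analyses of pharmacokinetic samples".
- Section 10.7: "All site e-mails to the team should be carefully worded to prevent unblinding the team, if possible". The same section places the unblinding of all participants after the last one has completed the study and the data have been cleaned.

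**The concern.** One group is asked both to judge relatedness without knowing the arm and to discuss whether a particular participant's drug concentrations call for an ADA test. The second task can undo the first. Section 6.3.13 has no firewall, masked identifier, unblinded delegate or deferral, and no other section supplies one.

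The primary endpoint depends on the core team's relatedness call. A team that knows a participant received cemiplimab may be readier to call a later event related, so any error would tend to run in one direction. Late events are to be expected. Section 2.2 says irAEs can appear several months after the last dose, and cites a possible hypophysitis 36 weeks after a single dose of an anti-PD-L1 antibody. Such events could fall after a PK-driven discussion of the same participant.

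**Working it through.** The plan gives no figure to reproduce. The check has four steps.

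**1. Is it the same body?** Sections 6.3.13, 7.4 and 10.2.1.1 all name the core team (section 7.4 calls it the core protocol team). No subgroup is carved out for the ADA discussion.

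**2. Can the two tasks overlap in time?** Assays may start once a cohort has completed week 12, and the endpoint runs to week 48. That leaves up to 48 − 12 = 36 weeks in which relatedness calls can follow a PK discussion.

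**3. Does a PK profile reveal the arm?** Placebo is diluent only (section 5.2), so its true concentration is zero. For active treatment I used a one-compartment linear approximation, C = (dose/V) × 2^(−t/half-life), summed over the two infusions. Inputs:

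- V = 5.20 L (section 11.0)
- half-life 19.2 days (section 2.2, steady state, solid tumors)
- an assumed 70 kg participant: 22, 70 and 210 mg from the section 5.2 dose tables
- infusions at days 0 and 42

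Dose/V gives 4.23, 13.46 and 40.38 mcg/mL. The decay factor over 42 days is 2^(−42/19.2) = 0.2195, and over 84 days it is 0.0482.

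| Dose | Before the week 6 infusion | Week 12 |
|---|---|---|
| 0.3 mg/kg | 4.23 × 0.2195 = 0.9 | 4.23 × (0.2195 + 0.0482) = 1.1 |
| 1 mg/kg | 3.0 | 3.6 |
| 3 mg/kg | 8.9 | 10.8 |

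(All in mcg/mL; placebo 0.)

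The steady-state half-life may be too long for first doses. Section 11.0's baseline clearance of 0.325 L/day gives 0.693 × 5.20/0.325 = 11.1 days and a 42-day factor of 0.0724. The week 6 values then become 0.3, 1.0 and 2.9 mcg/mL. The assay limit is not stated, and target-mediated clearance could lower the 0.3 mg/kg values further. The samples taken within 15 minutes after each infusion would still separate the arms.

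In probability terms, 4:1 allocation gives P(active) = 12/15 = 0.80 before any PK is seen. With assumed assay sensitivity s and specificity c:

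- Drug quantifiable: 0.8s/[0.8s + 0.2(1 − c)]. With s = 0.90 and c = 0.99 this is 0.72/0.722 = 0.997; with c = 1 it is 1.
- Drug not quantifiable: 0.8(1 − s)/[0.8(1 − s) + 0.2c]. With s = 0.90 and c = 0.99 this is 0.08/0.278 = 0.29; with s = 1 it is 0.

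The team need not see a concentration. ADA testing prompted by a PK profile makes sense only for someone who received drug, so the request itself points to active treatment.

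**4. What does one changed call do?** With 12 active recipients in a dose arm, 1/12 = 8.3 percentage points. Section 10.6.1 analyses everyone exposed, so replacements would enlarge the denominator and make the step slightly smaller.

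**The case against.** The strongest reply is that section 6.3.13 only permits. It says the testing may be done, case by case, if deemed necessary. It sets no time and does not say that the core team receives concentrations. Read with section 10.6.2, unblinded laboratory staff could hold the profile. This stands in part: disclosure is conditional, not certain. But the text puts the discussion with the core team and nothing delays it, so a site or laboratory following it as written could disclose an arm.

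Use may also be rare. Section 11.0 reports treatment-emergent ADA in 5/398 (1.26%) of oncology patients, with no altered PK in those affected. Applied to 36 active recipients this is 36 × 0.0126 = 0.45 cases. That is only indicative, because 0.3 mg/kg was not studied there and PK-prompted queries need not equal ADA-positive results. Moreover, 4:1 allocation already makes active treatment 80% likely. Both points limit the size of the problem without removing the conflict.

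Several stronger readings are tempting, but the documents do not support them:

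- **That section 6.3.13 contradicts section 10.6.2.** Section 10.6.2 permits early unblinding of designated laboratory staff and does not say that nobody else may be unblinded. The conflict is with the blinded relatedness role.
- **That the RO rule discloses arms to the core team.** Section 11.2.1 says "Determination of the need to assay certain/all samples will be based on the serum cemiplimab concentration seen", as does SOE footnote 3 in substance, but neither names the core team for that decision.
- **That SOE footnote 1 has the same fault.** Its trigger is an incomplete infusion, which says nothing about arm.
- **That relatedness is the endpoint's only subjective part.** Section 8.0 also leaves the classification of an event as an irAE to clinical judgement.
- **That pause and escalation decisions are equally exposed.** Assays start only after week 12, when the cohort's scheduled infusions are past. Under sections 10.4.1 and 10.5 the unblinded SMC also reviews relatedness.
- **That one changed call on pooled placebo (1/9) is a comparable risk.** A PK-prompted ADA query would ordinarily not arise for a placebo recipient.

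**Conclusion.** The point holds in conditional form. The protocol authorises a step that, if taken before the section 10.7 unblinding, would in effect disclose the arm of each participant discussed to the body judging relatedness for the primary endpoint. It affects only those participants, and mainly events judged between week 12 and week 48. It does not show that any assignment will be revealed, or that the trial as a whole loses its blind.

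The number affected is probably small, and the protocol sets no limit on it. Each changed call for an active recipient shifts that dose arm by up to 8.3 points. This requires the participant to have a qualifying event after the discussion and the call to change because of what was learned; the documents give no basis for the probability of either. The unblinded SMC is a partial safeguard for pause and escalation, but section 10.2.1.1 gives the primary endpoint none. The conclusion that PK identifies arm rests on drug-free placebo and an assay able to detect the predicted levels. It is least certain for late samples at 0.3 mg/kg. The wording should be corrected.

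**What to change.** In section 6.3.13, do one of the following:

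- assign PK-triggered ADA decisions to the designated unblinded laboratory staff of section 10.6.2, or to similarly designated pharmacology staff, who take no part in AE adjudication; or
- defer these decisions until all relatedness judgements through week 48 are final.

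In either case, state that no individual cemiplimab concentration and no PK-triggered assay request reaches the core team before the section 10.7 unblinding. As a precaution, apply the same statement to concentration-triggered RO assays (section 11.2.1 and SOE footnote 3). SOE footnote 1 needs no change.

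The cost is a wording amendment. No extra samples are needed, and section 10.6.2 already provides for unblinded laboratory staff. The core team loses input on a few reflex assays, or these are run later from stored serum.
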